3. Privacy:

Personal data will be collected from subjects. The data will be saved under a unique subject number, which will remove personal identifying information from the research data. Data will be secured under a password protected computer in a locked office of the PI.

28) If applicable, describe any group harms (i.e., research that focuses on a specific group or population):

RESPONSE: NA

29) Do you anticipate any circumstances in which a “breach of confidence” associated with a mandated disclosure (e.g. reporting abuse to authorities) may occur as part of this study?

RESPONSE: No we do not anticipate a breach of confidence

30) In the view of the PI, what risk classification (taking into consideration the probability and magnitude of harm) is appropriate for the proposed research?

Minimal Risk Greater than Minimal Risk Unknown

Minimal risk means the probability and magnitude of harm or discomfort anticipated in the research are not greater in and of themselves than those ordinarily encountered in daily life or during the performance of routine physical or psychological examinations or tests.

31) Please explain why you feel this category is appropriate based on the definition above (when more than minimal risk describe the likelihood and seriousness of such risks):

RESPONSE: In patients that are randomized to receive post operative antibiotics, there is a risk of adverse reaction to augmentin as detailed above. For patients that are randomized to placebo, there is a risk of post operative infection as detailed above as well. We believe the study is low risk to participants, however as defined above, it is more than the risk encountered in daily life.

32) What provisions are in place to minimize harm or discomfort?

RESPONSE: Patients are seen one week after surgery to undergo endoscopic evaluation to ensure that the patient is healing well without evidence of infection. At all times during the day they can call the sinus center to speak to a nurse if they have any concerns. At night there is a resident on call to answer questions and the MEEI ED is always open.

ALTERNATIVES

33) Describe any alternatives, especially other treatment(s) that are available to potential patients outside of the research:

RESPONSE: If patients do not elect to enroll in the study, they would receive standard post-operative care. They would be prescribed antibiotics at the discretion of the surgeon.

BENEFITS

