### **Statistical Analysis Plan**

The primary endpoint was the overall change in SNOT-22 scores from baseline to the final study visit. Secondary outcomes included the change in LK Endoscopic Score from the same time points, as well as rates of post-operative infection. Additional exploratory analyses included the effect of baseline clinical factors, including baseline sinus culture results, history of prior sinus surgery, comorbid asthma, and presence of nasal polyps.

The primary outcome and secondary outcome were analyzed using a repeated-measures analysis of variance (ANOVA) to assess for a group x time interaction on clinical scores. For the secondary analysis of the primary outcome, this model was modified to include baseline clinical covariates in a repeated-measures analysis of covariance (ANCOVA).

The achieved power for non-inferiority was calculated via the same methods as the prospective power analysis. Rather than an *a priori* estimate of standard deviation in scores, the achieved power was based on the actual number of randomized subjects and the actual pooled standard deviation of post-treatment SNOT-22 scores in the two groups. The non-inferiority margin was 9 units on the SNOT-22.

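### Baseline SNOT-22 is not named as a covariate in any model; with two time points, the primary group x time test is an unadjusted change-score comparison and gives up precision against the 9-unit margin.

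*SAP*

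**What the plan says.** All the relevant text on analysis is in the three paragraphs of the SAP.

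- **Endpoint (paragraph 1).** "The primary endpoint was the overall change in SNOT-22 scores from baseline to the final study visit". For the endoscopic score: "Secondary outcomes included the change in LK Endoscopic Score from the same time points".
- **Primary model (paragraph 2).** The outcomes were "analyzed using a repeated-measures analysis of variance (ANOVA) to assess for a group x time interaction on clinical scores". No covariate is mentioned.
- **Adjusted model (paragraph 2).** For a secondary analysis of the primary outcome only, "this model was modified to include baseline clinical covariates in a repeated-measures analysis of covariance (ANCOVA"). These covariates are not listed.
- **Baseline factors that are named (paragraph 1, as exploratory analyses).** "baseline clinical factors, including baseline sinus culture results, history of prior sinus surgery, comorbid asthma, and presence of nasal polyps". Baseline SNOT-22 is not among them.
- **Margin (paragraph 3).** "The non-inferiority margin was 9 units on the SNOT-22".

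Neither document states how many visits enter the repeated-measures model. The Protocol mentions one post-operative visit under Question 32: "Patients are seen one week after surgery to undergo endoscopic evaluation". It does not say whether SNOT-22 is collected then, or whether that is the final visit. Question 11 gives a total of 140 adults.

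**The concern.** In the primary model the baseline score appears only as the first level of time. With two time points, the group x time interaction then subtracts each patient's baseline in full, as if the slope of final on baseline score were 1. When the true slope is lower, full subtraction adds baseline noise to the comparison, and regression on baseline avoids that.

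This is a matter of precision, not bias. It matters because the trial asks whether a disadvantage of 9 SNOT-22 units can be excluded, and the width of the confidence interval decides how clearly that can be answered. The baseline score is already collected because the endpoint needs it, so the lost precision could be recovered without new data.

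**Working it through.** **What can be reproduced.** The planned total of 140 cannot be checked, because the available text gives no alpha, power or SD with it. With 70 per arm, margin 9 and true difference 0, the implied SD is 9 x sqrt(70/2) / (z_alpha + z_power):

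| One-sided alpha | SD implied at 80% power | SD implied at 90% power |
|---|---|---|
| 0.025 | 19.0 | 16.4 |
| 0.05 | 21.4 | 18.2 |

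An SD of 20 is therefore a reasonable illustration, but it remains an assumption.

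**Inputs.** From the documents: margin 9 (SAP), total 140 (Protocol Question 11), two randomised groups. Assumed: two analysed time points, 1:1 allocation, true difference 0, one-sided 0.025, SD 20 at both visits, and baseline-to-final correlation r from 0.3 to 0.8.

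**Step 1: the identity.** With two time points, the group x time F equals the square of the t statistic on change scores. On a simulated data set both were 2.776.

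**Step 2: variances.** Per patient, with SD0 at baseline and SD1 at the final visit:

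- change score: SD0² + SD1² − 2r·SD0·SD1
- baseline-adjusted: SD1²(1 − r²)

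With equal SDs the ratio adjusted/change is (1 − r²) / [2(1 − r)] = (1 + r)/2. The standard error is sqrt(2·Var/n) with n analysed per arm. The half-width is t(0.975) x SE. Power uses the noncentral t with 2n − 2 df (change) or 2n − 3 df (adjusted).

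For r = 0.5, n = 70:

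- change: variance 400, SE sqrt(800/70) = 3.38, half-width 6.68
- adjusted: variance 300, SE sqrt(600/70) = 2.93, half-width 5.79

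**Step 3: results at SD 20, 70 per arm.**

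| r | Variance ratio | Half-width, change → adjusted | Power against 9, change → adjusted |
|---|---|---|---|
| 0.3 | 0.65 | 7.9 → 6.4 | 61% → 79% |
| 0.5 | 0.75 | 6.7 → 5.8 | 75% → 86% |
| 0.7 | 0.85 | 5.2 → 4.8 | 93% → 96% |
| 0.8 | 0.90 | 4.2 → 4.0 | 98.7% → 99.3% |

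A change-score analysis would need about 140/0.65 = 215, 140/0.75 = 187 or 140/0.85 = 165 patients to match an adjusted analysis of 140 at r 0.3, 0.5 or 0.7. Simulation (20,000 trials each) gave 60.5% and 78.8% at r 0.3, and 75.1% and 85.9% at r 0.5.

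**Step 4: varying the assumptions (power, change → adjusted).**

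| Setting | r 0.3 | r 0.5 | r 0.7 |
|---|---|---|---|
| 63 analysed per arm (10% loss), SD 20 | 56% → 75% | 71% → 82% | – |
| 56 analysed per arm (20% loss), SD 20 | 51% → 70% | 66% → 78% | 86% → 91% |
| One-sided 0.05, 70 per arm, SD 20 | 72% → 87% | 84% → 92% | – |
| SD 15, 70 per arm | – | 94% → 98% | 99.5% → 99.9% |
| SD 25, 70 per arm | – | 56% → 69% | – |

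With unequal SDs the adjusted variance is never the larger. At SD0 25 and SD1 20 the ratio runs from 0.50 (r 0.3) to 0.64 (r 0.8). At SD0 20, SD1 25 and r 0.8, the slope is 0.8 x 25/20 = 1. Both variances are then 225 and power is 94.1% either way, so the gain is nil.

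**Step 5: would the secondary ANCOVA supply the adjustment?** A time-constant covariate entered only as a main effect shifts both visits equally and cancels from the group x time contrast. One simulated data set (70 per arm, r 0.5) shows this:

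| Model | SE | F |
|---|---|---|
| Plain repeated-measures ANOVA (= t test on change) | 2.980 | 6.547 |
| Adding baseline as a main effect only | 2.980 | 6.547 |
| Adding baseline x time (= ANCOVA of final score) | 2.582 | 2.592 |

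So even if baseline SNOT-22 is among the unlisted covariates, it sharpens the test only if it is crossed with time. The SAP mentions no such term.

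**The case against.** The strongest reply is that nothing here is an error. A group x time test is a valid analysis of a change endpoint, and preferring ANCOVA is a choice between two unbiased methods. That is correct, and the point claims no more than lost precision.

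Second, the change-score identity needs exactly two analysed time points, and the SAP does not give the number. This stands as a condition. With three or more visits the interaction has several degrees of freedom and the figures above do not apply.

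Third, SD, correlation, alpha, allocation and attrition are all assumed, and the gain runs from nil to about 18 points across the settings shown. At SD 20 the half-width is below 9 in every case in the main table, and also at 56 per arm with r 0.3 (8.86 unadjusted, 7.15 adjusted). Either analysis would therefore exclude 9 units if the observed difference were zero. That is true, but observed differences vary. At r 0.3 and 70 per arm, the interval excludes 9 only if the observed difference against placebo is below 9 − 7.91 = 1.1 units, compared with 9 − 6.38 = 2.6 after adjustment.

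Fourth, the SAP states no comparison of a confidence interval with the margin, so the benefit is seen only if one is reported. This is fair, and the remedy therefore asks for that interval.

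Finally, the list of baseline factors is open-ended, so baseline SNOT-22 may have been used. The documents neither name nor exclude it. Listing the covariates would settle this.

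**Conclusion.** The point holds as a conditional statement about precision. Baseline SNOT-22 is not named as a covariate in either document. If two time points are analysed, the primary test is the unadjusted change-score comparison. Under the stated assumptions at SD 20 and 70 per arm, adjusting for baseline removes 10% to 35% of the variance for r between 0.8 and 0.3. The power gain against the 9-unit margin is about 18 points at r 0.3, 11 at r 0.5, 3 at r 0.7 and under 1 at r 0.8. It vanishes when the slope on baseline is 1. The documents do not show which of these applies, and they cannot show that the trial's conclusion would change. The change should still be made: the adjusted estimate is also unbiased, uses data already in hand, and bears directly on whether the margin can be excluded. Confidence is medium, because the number of visits, the SD and the correlation are not given.

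**What to change.** 1. Estimate the treatment difference in final-visit SNOT-22 with baseline SNOT-22 as a covariate. With two time points, a repeated-measures model with a baseline x time term gives the same estimate and standard error; a baseline main effect alone does not help.
2. If more visits are analysed, use a constrained-baseline longitudinal model and take the final-visit contrast.
3. Report the difference with its 95% CI beside the 9-unit margin. Also report a baseline-adjusted difference with its 95% CI for the LK endoscopic score, using that score's own baseline.
4. State the number of time points in the model. List the covariates of the secondary ANCOVA, say whether baseline SNOT-22 is one of them, and say whether it is crossed with time.

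The cost is one covariate and one degree of freedom in the two-time-point model, with no new data. The SAP is written in the past tense and refers to actual subject numbers and SDs. If outcomes have been seen, keep the stated primary analysis and report the adjusted estimate as one labelled sensitivity analysis.

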7) Delegation of Significant Study-Related Tasks- If non-physicians are tasked to assess clinical response to an investigational therapy, provide medical care to subjects during the course of the study, assess inclusion/exclusion criteria, and evaluate adverse events, list their names in the table below and complete:

Name	Delegated Tasks	Qualifications- Licensing, or Certification	Training
[name] / [name], follow-up, evaluation for adverse reactions, data collection	MD	Residency and fellowship training in otolaryngology and rhinology
Pharmacy staff (supervised by [name])	Distribution of study drug	Pharm D	Doctorate in pharmacy

8) Indicate all MEE sites where research activities occur:

- Boston-MEEI [name]
- Boston Longwood Medical Area – [name]
- Boston-SERI [name]
- Braintree - [name]
- Concord - [name]
- Duxbury - [name]
- East Bridgewater - [name]

- Milton - [name]
- Newton - [name]
- Quincy - [name]
- Stoneham - [name]
- Stoneham - Retina Consultants-[name]
- Weymouth - [name]

9) Are there any non-MEE sites involved in this study? YES NO (If NO, skip to question 11)

IF YES, Is MEE the lead site or coordinating center? YES NO

10) In the table below, list each non-MEE sites where research activities will occur, and the status of IRB review at each site (indicate if the intent is for MEE to serve as the IRB of record for all study sites (cede review) or if IRB review will be required at other sites:

Non-MEE Sites	IRB Review Status (i.e., review pending, approved, seeking cede review)

SUBJECT INFORMATION

11) In the table below, please indicate age range, gender, total number of subjects to be enrolled at MEE, and if multi-site, total number for the study:

	Age Range	Total Number at MEE	Total Number for the Study (if multi-site)
Adults (over 18)	18- no limit	140	140
Children (under 18)	NA	0	

12) Is a gender being excluded from this study? YES NO

IF YES, provide scientific justification:

Response:

13) Select all populations that may/will be enrolled (will not be excluded from the study) below. For some populations you may be asked to provide additional information.

- Pregnant Women
- Employees/Staff of MEEI or SERI-please specify:
- Healthy Controls

- Students/ Residents/ Fellows or other trainees
- Children
- Prisoner
- Non-English Speaking Subjects

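### The primary endpoint is change from baseline to the final visit, but the group × time test is not limited to those two times; if an intermediate visit is modelled, it tests something else

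*SAP*

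**What the plan says.** The first paragraph of the SAP fixes the endpoint: "The primary endpoint was the overall change in SNOT-22 scores from baseline to the final study visit". It defines the endoscopic endpoint in the same way: "Secondary outcomes included the change in LK Endoscopic Score from the same time points".

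The second paragraph gives the analysis for both, a "repeated-measures analysis of variance (ANOVA) to assess for a group x time interaction on clinical scores". It does not say which visits are levels of the time factor, and it names no contrast within the interaction. The third paragraph adds: "The non-inferiority margin was 9 units on the SNOT-22".

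The Protocol text available gives no SNOT-22 schedule. The one dated post-operative visit it mentions is in Question 32, on minimising harm: "Patients are seen one week after surgery to undergo endoscopic evaluation". It does not say whether SNOT-22 is completed there, whether that visit enters any model, or whether it is itself the final visit.

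**The concern.** The endpoint is one number per patient, and its comparison between arms is one contrast. A group × time interaction matches that contrast only when time has two levels. With three or more levels, it asks whether the arms' mean profiles differ in shape anywhere over follow-up.

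Two things would then be at stake. First, the p-value attached to the primary endpoint could be driven by a temporary difference at an intermediate visit even though the change to the final visit is the same in both arms. Second, an interaction F-test on two or more degrees of freedom yields no single between-arm difference with a confidence interval, and that is the quantity to be compared with the 9-unit margin.

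**Working it through.** **Inputs from the documents.** Planned enrolment is 140 (Protocol Question 11: "18- no limit 140 140"). The margin is 9 SNOT-22 units (SAP, third paragraph). No SD value appears; the SAP's only reference to a planning value is the phrase "Rather than an *a priori* estimate of standard deviation in scores".

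**Assumptions, not in the documents.** 1:1 allocation (70 per arm), 5% level for the F-test, no dropout, equal SD and equal correlation ρ between all visits, SD 15 to 25, ρ 0.3 to 0.7.

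**Step 1: the plan's own figure.** The total of 140 cannot be reproduced, because SD, alpha and power are not in the text. Working backwards for non-inferiority with a true difference of zero, SD = 9 × √(70/2) / (z for alpha + z for power). At one-sided 0.025 and 80% power this is 53.25 / 2.80 = 19.0. The other common choices give 16.4 (0.025, 90%), 21.4 (0.05, 80%) and 18.2 (0.05, 90%). An illustrative SD of 20 is therefore reasonable, but it remains an assumption.

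**Step 2: two times.** In simulated data with baseline and final visit only, the interaction F equals the squared t statistic on the change score to within rounding error (about 1e-14). The two tests are the same.

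**Step 3: three times, gap at the middle visit only.** With n per arm, T visits and d_t the true arm difference at visit t, the interaction F has T−1 and (2n−2)(T−1) degrees of freedom. Its noncentrality is λ = (n/2) × Σ(d_t − mean d)² / [SD² (1−ρ)].

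For the profile (0, 9, 0) the mean is 3, so the sum of squares is 9 + 36 + 9 = 54, and (70/2) × 54 = 1,890. The degrees of freedom are 2 and 138 × 2 = 276.

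| SD | ρ | λ | Interaction test rejects |
|---|---|---|---|
| 20 | 0.3 | 1,890/280 = 6.75 | 63% |
| 20 | 0.5 | 1,890/200 = 9.45 | 79% |
| 20 | 0.7 | 1,890/120 = 15.75 | 95% |
| 25 | 0.3 | 1,890/437.5 = 4.32 | 44% |
| 15 | 0.7 | 1,890/67.5 = 28.0 | 99.8% |

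The baseline-to-final contrast has a true value of zero here, so it rejects at its nominal 5%. Simulation at SD 20, ρ 0.5 (10,000 trials) gave 79.3% for the interaction and 4.8% for the contrast. With four visits and profile (0, 9, 0, 0), it gave 78.5% against 5.2%.

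A smaller middle-visit gap of 5 units gives 31% at SD 20, ρ 0.5, and 16% to 75% over the whole grid.

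**Step 4: no difference at any visit.** The three-visit interaction test rejected in 4.6% of simulated trials. Type I error is kept for the hypothesis of no difference in profile, but that is not the null hypothesis of the stated endpoint.

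**Step 5: real effects at the final visit** (SD 20, ρ 0.5). The two-time test of a 9-unit final difference has λ = 35 × 40.5 / 200 = 7.09 on 1 df and power 75.3%. With three visits:
- Effect at the final visit only, (0, 0, 9): λ = 9.45 on 2 df, power 78.7%.
- Gradual effect, (0, 4.5, 9): λ = 7.09 again but on 2 df, power 65.6%.

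Power for the stated endpoint can therefore rise or fall with the trajectory.

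**The case against.** The strongest objection is that no third time is shown to be modelled. The SAP names only baseline and the final visit, and the LK endpoint refers back to the same pair. The power paragraph uses a pooled SD of post-treatment scores, which fits a single post-treatment score. On that reading, time has two levels and the test is exactly right. This stands as far as it goes: the documents lean towards two times. But those sentences define endpoints and a power calculation; none says which visits enter the ANOVA.

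Three stronger readings are tempting, and the documents do not support them.

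- A reader might infer that the one-week visit is in the model. Question 32 describes an endoscopic check for healing and infection. It mentions neither SNOT-22 nor any analysis, so it makes an intermediate time possible and no more.
- A reader might infer that a final visit implies an earlier post-operative score. It need not: Question 37 describes a preoperative visit, and final may simply contrast with that. Parts of both documents are also not in the available text, so a visit list may exist elsewhere.
- A reader might infer that the interaction test tilts the trial towards finding no difference. Step 5 shows the opposite for an effect confined to the final visit. The direction depends on the trajectory.

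It is also fair to say that a gap as large as the whole margin at one visit, followed by exact equality, is an extreme case. The 5-unit result shows how the size shrinks.

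**Conclusion.** The point holds conditionally. The SAP states a single baseline-to-final endpoint but specifies a test that matches it only if time has exactly two levels, and it does not say that it has. If it does, there is no error in the result. If any intermediate visit is included, the primary p-value no longer tests the primary endpoint: in the illustrative (0, 9, 0) case it rejects in 44% to 99.8% of trials across the assumed SDs and correlations, where the right answer is 5%.

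Those percentages rest on the assumed SD, correlation structure, allocation and effect profile. The assumptions set their size; the mismatch itself follows from the form of the test. The available text does not settle which case applies, so this is a low-cost improvement to make rather than a demonstrated error.

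**What to change.** In the second paragraph of the SAP, list the visits that form the time factor and say which is final. Make the primary analysis the single 1-df between-arm contrast in SNOT-22 change from baseline to the final visit, reported with its confidence interval, since that interval can be set against the 9-unit margin. The contrast can come from a model holding only those two times, or from one with visit as a categorical factor and unstructured covariance. Do the same for the LK score. Keep any overall group × time F-test as supportive only.

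The cost is about one sentence and no new data. Differences confined to intermediate visits would no longer count towards the primary test, which is what the endpoint definition already implies. If two times were already used, the point estimate and p-value do not change and the sentence simply records what was done.

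### The adjusted SNOT-22 analysis does not say how covariates enter; as main effects only, with complete data, it returns the unadjusted group x time result exactly

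*SAP*

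**What the plan says.** All the relevant text is in the SAP, under Statistical Analysis Plan. The endpoint is a change: "The primary endpoint was the overall change in SNOT-22 scores from baseline to the final study visit". The analysis is a "repeated-measures analysis of variance (ANOVA) to assess for a group x time interaction on clinical scores". For the secondary analysis of that outcome, "this model was modified to include baseline clinical covariates in a repeated-measures analysis of covariance (ANCOVA".

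The covariates are not named in that sentence. The only baseline clinical factors the SAP lists are "baseline sinus culture results, history of prior sinus surgery, comorbid asthma, and presence of nasal polyps", and they appear under a separate exploratory aim: "Additional exploratory analyses included the effect of baseline clinical factors". That these four are the ANCOVA covariates is an inference, though nothing else in the text fits. All four are measured once and are constant within a patient.

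The SAP does not say whether covariates enter as main effects or with time interactions, how many visits the model contains, or how missing visits are handled. The margin is given: "The non-inferiority margin was 9 units on the SNOT-22".

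**The concern.** A group x time interaction is a within-patient contrast, while a factor fixed at baseline varies only between patients. Entered as a main effect, such a factor can explain why one patient scores higher than another on average, but not why one patient changes more than another. An analysis labelled as adjusted could then adjust nothing that bears on the endpoint.

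Two things are at stake. The secondary analysis of the primary outcome may add no information, or it may give one of several different answers depending on how the model statement is written. The exploratory question about baseline factors may also be answered for the wrong quantity, namely SNOT-22 level averaged over visits instead of change.

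**Working it through.** **Inputs.** Endpoint, model and the 9-unit margin come from the SAP. The total of 140 comes from the protocol's subject table (question 11); 70 per arm assumes equal allocation. The available text gives no SD, baseline-final correlation, factor effects, alpha or power, so all of these are assumptions here.

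**The plan's own figure.** For non-inferiority with no true difference, n per arm = 2 SD² (z_alpha + z_power)² / 9². Solving for the SD at 70 per arm gives SD = 9 × √35 / (z_alpha + z_power):

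- One-sided 0.025: 19.0 at 80% power and 16.4 at 90%.
- One-sided 0.05: 21.4 at 80% power and 18.2 at 90%.

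So 140 is neither confirmed nor contradicted. The point does not depend on it.

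**Algebra.** Take two visits (t = 0, 1), arm G and baseline factor X:

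- Main effect only: Y = μ + αG + βt + γGt + δX + b + e. Subtracting visits within a patient gives change = β + γG + (e₁ − e₀). The term δX cancels. With complete data, γ, its SE and its p-value cannot move, and δ describes the mean of the two visits.
- With X x time: change = β + γG + θX + (e₁ − e₀). This is change regressed on arm and factor. Here γ can move, and θ is the factor's effect on change.

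**Numerical check.** Random-intercept models (REML) were fitted to simulated trials of 140 with four binary factors and no true arm effect. The assumed factor effects on change were -8, 8, 6 and 4 points. Entries are the group x time estimate at the last visit (SE; p).

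| Data set | Unadjusted | Main effects | Covariate x time |
|---|---|---|---|
| A, complete, 2 visits | -2.7775 (3.1397; 0.376) | -2.7775 (3.1397; 0.376) | -2.7646 (2.9084; 0.342) |
| A, complete, 4 visits | -1.3909 (3.0155; 0.645) | -1.3909 (3.0155; 0.645) | -1.1322 (2.9257; 0.699) |
| B, complete, 2 visits | 4.1413 (3.1362; 0.187) | 4.1413 (3.1361; 0.187) | 3.1348 (3.0655; 0.307) |
| A, 20% of follow-up missing, 2 visits | -3.8497 (3.5734; 0.281) | -3.7049 (3.5807; 0.301) | -2.7660 (3.3147; 0.404) |
| B, 20% of follow-up missing, 2 visits | 7.8035 (3.6607; 0.033) | 7.4990 (3.6342; 0.039) | 6.4898 (3.4980; 0.064) |

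With complete data the first two columns agree to numerical tolerance. Ordinary regression of change on arm and factors in data set A gives -2.7646 (SE 2.9083), as the algebra predicts. Over 300 complete two-visit trials, adding covariate x time terms moved the estimate by 0.98 units on average (maximum 3.96) and cut the SE by about 5%.

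**Precision from baseline SNOT-22.** With equal variances σ² at both visits and correlation r, the variance per patient is 2σ²(1 − r) for change and σ²(1 − r²) after conditioning on baseline. The ratio is (1 + r)/2: 0.65 at r = 0.3 and 0.75 at r = 0.5, a reduction of 35% or 25%.

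For scale, take SD 19 and 70 per arm:

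- r = 0.5: SE of the change contrast = √(361 × 2/70) = 3.21, so the 95% half-width is 6.3. After conditioning, SE = √(270.75 × 2/70) = 2.78 and the half-width is 5.5.
- r = 0.3: SE falls from √(505.4 × 2/70) = 3.80 to √(328.51 × 2/70) = 3.06, and the half-width from 7.4 to 6.0.

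A separate simulation (4,000 trials per setting) added the clinical factors to the ANCOVA. Its variance ratios against the group x time estimate were 0.68 and 0.76 (r = 0.3 and 0.5) with no factor effect on change, and 0.63 and 0.71 with an assumed 8-point effect. Most of the gain therefore comes from the baseline score.

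**The case against.** The strongest reply is that the SAP never says main effects only. A repeated-measures ANCOVA can carry covariate x time terms, and then the treatment result does change. That stands. A reader might infer that the adjusted result must repeat the unadjusted one, but the documents do not fix the specification, so the identity is conditional. It also needs complete data. If visits are missing and a mixed model keeps every row, even main effects shift the estimate a little (7.80 to 7.50 above). The shift is not adjustment of change in any useful sense, but it breaks the exact identity.

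A reader might also infer that the sponsor intends the adjusted analysis as proof of robustness and so offers false reassurance. The SAP does not present it that way, and it calls the factor analyses exploratory. Someone could draw that conclusion from a matching adjusted result, but the plan does not claim it.

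Nor should the whole precision gain be credited to the four clinical factors. It comes almost wholly from conditioning on baseline SNOT-22, a suggestion that would apply to the primary model as well.

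Finally, comparing change between randomized arms is valid, and a single clause could remove the ambiguity. Both are true. The clause would not recover the precision, however, and as written the sentence specifies either an empty adjustment or one of several analyses that can disagree.

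**Conclusion.** The point holds in conditional form. If the covariates enter as main effects only and the data are complete, the adjusted group x time estimate, SE and p-value are the unadjusted ones, and the covariate coefficients concern level, not change. That follows from algebra and needs no assumed values. If time interactions are included, or visits are missing in a mixed model, the result can differ. Under the assumed factor effects, covariate x time terms shifted it by about 1 unit on average and 4 at most, against a margin of 9.

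The 25-35% variance reduction from conditioning on baseline SNOT-22 rests on equal variances and a correlation of 0.3-0.5. Any further gain from the clinical factors is smaller and depends on their unknown effect on change. The simulated estimates say nothing about this trial's result. The primary unadjusted comparison is unaffected, so this is a change that should be made to a secondary analysis and not a threat to the main comparison.

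**What to change.** Replace the secondary model with an ANCOVA of final-visit SNOT-22 on arm, baseline SNOT-22, culture result, prior sinus surgery, asthma and polyps. Report the adjusted arm difference with its 95% CI against the 9-unit margin.

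If the repeated-measures form is kept, name the covariates, enter each with its interaction with time, and read factor effects from those interaction terms. In either case, state how missing visits are handled.

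The cost is a few lines of SAP text and a changed model statement; the SAP already plans to analyse all of these variables. Because the SAP is written in the past tense, the analysis may already have been run. In that case the revised model is a re-analysis of existing data and should be labelled as added afterwards.
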